- Assessment of AEs and concomitant medication (see Section 9.8)
- Assessment of body weight
- Physical examination including palpable tumor assessment (general appearance, skin, head, eyes, ears, nose, throat, lungs, breasts and axillae (if applicable including bi-dimensional measurement of cervical, supraclavicular, axillary and inguinal lymph nodes), cardiovascular system, back and spine, abdomen (if applicable including spleen size below the costal margin), extremities, infusion site, lymph nodes, and neurological examination).
- ECOG performance status
- Vital signs (pulse, blood pressure, temperature and respiratory rate)

- Response assessment should be repeated at 2nd, 4th, 5th and all subsequent follow-up visits and include:
 - Assessment by physical examination
 - CT of neck, chest, abdomen and pelvis. A PET scan should also be used for response assessment if CT does not provide a clear readout and if the lymphoma is expected to be PET-avid. Follow-up radiographic evaluations may be performed any time \pm 4 days of the planned visit.
 - Radiological evaluation in addition to the CT/PET of neck, chest, abdomen and pelvis are to be done as appropriate (for MRI, please see Section 10.6). Radiological evaluations for response assessment should be performed at least for any procedure performed at baseline.
 - Bone marrow aspiration and biopsy (only to be repeated if previous response was not CR)
- Laboratory assessments from blood sampling:
 - Haematology including CBC with differential and platelet count and serum chemistry
 - Coagulation
 - PK sample at the 1st, 2nd and 3rd follow-up visit only
 - Anti-MOR00208 antibodies at the 1st and 3rd follow-up visit only
 - Serum immunoglobulin levels
 - β -HCG pregnancy test for women of childbearing potential (only urine pregnancy test is to be done if regular follow-up visit coincides with maintenance treatment visit; otherwise, serum pregnancy test should be done)
 - If anti-HBc is positive: HBV-DNA as per assessment schedule. (Please see also Section 9.5.2.)
- Laboratory assessments from urine sampling: Urinalysis

10.4 MOR00208 Treatment and Study Procedures after Follow-up Visit 12

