10.6 Efficacy

Efficacy will be evaluated in terms of the ORR, SD, DoR, TTP, and PFS. The ORR will be evaluated using the revised IWG criteria (Cheson, 2007) and will be defined as the proportion of patients with CR and PR (CR+PR).

The DoR will be the time from first meeting of criteria for response (ie, CR or PR) to first documentation of relapse or progression.

The TTP is defined as the time from study entry (first dosing) until documented lymphoma progression or death as a result of lymphoma. Deaths from other causes are censored at the time of death.

PFS is defined as the time from study entry (first dosing) until lymphoma progression or death as a result of any cause.

Response criteria are provided in [Section 17.4](#).

CT or PET Examination, or Further Radiological Examinations

CT: For all patients, CT neck/chest/abdomen/pelvis is required as indicated in the schedule of assessments at baseline and at all time points when a radiographic response assessment is performed.

PET: For patients with DLBCL and patients known or expected to have PET-avid lymphomas, a PET scan should be performed at baseline in addition to the CT scan. At the subsequent visits, PET should be done in DLBCL patients or if at baseline the lymphoma was PET-avid, but can be omitted if PET definitely would not change the response assessment according to the clinical judgement of the investigator (eg, CT already shows progressive disease).

MRI may be used in lieu of CT for subjects with contraindications to administration of contrast agents or due to other medical reasons (at the same time windows as CT), or in addition to CT at the discretion of the investigator (in this case, MRI may be performed as/when appropriate). The method used at baseline should be used throughout the study unless otherwise medically indicated.

Additional radiographic evaluations: are to be done, as appropriate. Follow-up radiographic evaluations will be performed for any procedures performed at baseline visit at the end of Cycle 2 and 3 (if applicable) and at the second, fourth and every further follow-up visit. Follow-up radiographic evaluations may be performed anytime \pm 4 days of the planned visit. If

a patient discontinues from the study before any response assessment, if possible a response evaluation will occur approximately one month after the patient discontinues from the study.

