14.5.1 Secondary Efficacy Variables and Analyses

The proportion of patients in each subtype with stable disease (SD) will be summarized after the second cycle.

The DoR will be the time from first meeting of criteria for response (ie CR or PR) to first documentation of relapse or progression.

The TTP is defined as the time from study entry (first dosing) until documented lymphoma progression or death as a result of lymphoma. Patients not experiencing a progression will be censored at the last NHL assessment. Deaths from other causes are censored at the time of death. The data will be summarized using Kaplan-Meier estimates.

Progression-free survival is defined as the time from study entry (first dosing) until lymphoma progression or death as a result of any cause. Patients not experiencing a progression or death will be censored at the last NHL assessment. The data will be summarized using Kaplan-Meier estimates.

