Duration of response (Investigator): Duration of response will be defined as the time from date of first response (CR or PR) until first date that recurrence or progressive disease is objectively documented. The duration of response will be calculated in the subgroup of all patients showing any response; confirmation of response will not be required. Patients who showed a response but did not show PD or recurrence until end of study or before study discontinuation (i.e. patients who are at least stable at their last tumor assessment) are considered censored at the timepoint of last response assessment. Deaths due to causes other than progression of disease are to be reported as SAEs and are censored for duration of

Statistical Analysis Plan Final Version 4.0

response analysis at the date of last tumor assessment before death. The cause of death has to be recorded as free text by the Investigator on the eCRF study completion page. If the cause of death does not explicitly state whether death is related to progression of disease, a query will be raised to ask the investigator to classify the relationship to disease (yes/no). Morphosys Drug Safety will assess the causality of the SAE by reviewing the corresponding SAE documents.

Time to response (Investigator): Time to response will be defined as the time from Cycle 1, Day 1 (first administration of study drug) until the date of first response (CR or PR). Patients who do not have a response to treatment will be censored at the date of their last tumor assessment.

Time to progression (Investigator): Time to progression is defined as the time from Cycle 1, Day 1 (first administration of study drug) until date of first tumor progression (which is entered in the tumor assessment module). Patients who do not show any documented progression (which is entered in the response assessment module of the eCRF) before the end of study or before study discontinuation or before death are considered censored using the last date with a tumor assessment as censoring date (irrespective of when the patient died). Deaths due to causes other than disease progression are censored.

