Progression-free survival (Investigator): Progression-free survival is defined as the time from Cycle 1, Day 1 (first administration of study drug) until date of first tumor progression (which is entered in the response assessment module of the eCRF) or date of death from any cause. If the patient does not show any documented progression (which is entered in the tumor assessment module) before death, the date of progression will be the date of death if death occurs within 2 months after the last date with a tumor assessment. If death occurs after 2 months after the last date with a tumor assessment or the patient did not progress or die until end of study or before withdrawal, the patient will be analyzed as censored using the last date with a tumor assessment as censoring date.

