12. CHANGES FROM PLANNED ANALYSIS

The PK population was originally defined in the protocol as consisting of all patients who have sufficient pharmacokinetic data to characterize the time course of MOR00208 in serum for the first study drug administration. This is changed in the SAP to include all patients who have at least one quantifiable serum MOR00208 concentration (see section 6).

The protocol did not specify ORR as a result of central read as an endpoint, but this has now been added to the secondary endpoints of the study.

The protocol specified that “Evaluation of AEs and ORR stratified by baseline CD19 expression on malignant lymphoma cells” was one of the secondary endpoints. This is no longer considered an endpoint as it has not been possible to measure CD19 expression in sufficient cases for such an analysis to be meaningful.

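### The SAP's time-to-progression rule drops death from lymphoma, which the protocol counts as an event, and Section 12 does not declare the change; TTP may be overstated

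*SAP*

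**What the plan says.** Protocol 14.5.1 states: "The TTP is defined as the time from study entry (first dosing) until documented lymphoma progression or death as a result of lymphoma". Protocol 10.6 defines the event in the same way and adds: "Deaths from other causes are censored at the time of death". Section 14.5.1 also says that patients without progression are censored at their last lymphoma assessment.

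SAP 7.3.4.1 defines investigator TTP as time from first dose to first tumour progression entered in the eCRF, with no death component. Patients without documented progression before end of study, discontinuation or death are "considered censored using the last date with a tumor assessment as censoring date (irrespective of when the patient died"). The paragraph then closes with: "Deaths due to causes other than disease progression are censored". SAP 7.3.4.2 gives the same rule for the central read, without that closing sentence.

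SAP Section 12 lists three changes from the protocol: the PK population, the added central-read ORR ("The protocol did not specify ORR as a result of central read as an endpoint") and the dropped CD19 stratification. TTP is not among them.

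**The concern.** A death from lymphoma before any recorded progression is a failure under the protocol and a censored observation under the SAP. The disease itself causes that censoring, so it is informative, and Kaplan-Meier then overstates time to progression. The SAP also moves the censoring date for other-cause deaths from the death back to the last assessment.

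The closing sentence of the investigator rule makes the text ambiguous. Either it is redundant, because all such deaths are already censored, or it implies that deaths from progression are events. It names no event and no event date, so two programmers could code it differently.

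Protocol 14.13 requires departures from the planned analysis to be described with reasons in the study report. A change missing from Section 12 could be missed there too.

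**Working it through.** The documents state no TTP figure, so there is none to reproduce. The check compares the rules and then sizes the effect under stated assumptions.

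**Rules side by side**

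| Patient without documented progression | Protocol 10.6, 14.5.1 | SAP 7.3.4.1 and 7.3.4.2 |
|---|---|---|
| Dies of lymphoma | Event at death | Censored at last tumour assessment |
| Dies of another cause | Censored at death | Censored at last tumour assessment |
| Alive | Censored at last assessment | Censored at last assessment |

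**Scan days** (Protocol 10.2, 10.3 and Table 2). Cycle 2 Day 28 is day 56. Cycle 3 starts two weeks after Cycle 2 Day 22 (day 50), so on day 64, and Cycle 3 Day 28 is day 91. Follow-up visit 1 is 91 + 28 = 119, visit 2 is 119 + 42 = 161 and visit 3 is 161 + 42 = 203. "Response assessment should be repeated at 2nd, 4th, 5th and all subsequent follow-up visits", so visits 1 and 3 have no scan. Visit 4 is day 294, visit 5 day 385 and visit 6 day 476, then every 183 days.

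**Model (assumed).** TTP is exponential. Each event is a lymphoma death without documented progression with probability p, which is not in the documents. Progression is dated when it occurs. Under the SAP rule such a death is censored at the last scan before it, or at day 0 if there is none (the SAP gives no rule for that case). There are 400,000 simulated patients and no other-cause deaths.

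| p | Median, protocol (months) | Median, SAP (months) | Progression-free at 12 months, protocol | Same, SAP |
|---|---|---|---|---|
| 0% | 6.0 | 6.0 | 25.0% | 25.0% |
| 5% | 6.0 | 6.3 | 25.0% | 26.5% |
| 10% | 6.0 | 6.6 | 25.0% | 28.1% |
| 20% | 6.0 | 7.2 | 25.0% | 31.7% |
| 30% | 6.0 | 8.1 | 25.0% | 36.0% |

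At p = 30%, a true median of 3 months reads 4.0 and one of 12 months reads 16.7.

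Analytic check: if these deaths were censored at death, the median would be 6/(1 − p), which is 6/0.70 = 8.6 months at p = 30%. Censoring at the earlier scan gives 8.1. The overstatement therefore comes from dropping the event; the earlier censoring date offsets a little of it.

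If progression is dated only at scans, the 12-month values (protocol against SAP) are 32.4% and 34.4% at p = 5%, and 30.4% and 44.0% at p = 30%.

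**A cohort of planned size (assumed pattern).** Of 30 patients, 12 progress at day 56, 5 at day 91 and 3 at day 161; k die of lymphoma without documented progression; 10 − k are censored late. With k = 4, all deaths before 12 months, the protocol rule gives (30 − 24)/30 = 20.0%. The SAP rule gives:

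- Deaths before day 56, censored at day 0: (14/26) × (9/14) × (6/9) = 6/26 = 23.1%.
- Deaths between days 91 and 161, censored at day 91: (18/30) × (13/18) × (6/9) = 28.9%.
- Deaths after day 161, censored at a scan on or after day 161: (18/30) × (13/18) × (10/13) = 33.3%.

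The overstatement is 3.1, 8.9 and 13.3 percentage points. At k = 0 both rules give 33.3%.

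**Does PFS cover the gap?** SAP 7.3.4.1 also censors PFS at the last assessment "If death occurs after 2 months after the last date with a tumor assessment". Taking 2 months as 61 days, the days of each scan gap outside the window are 0 of 56, 0 of 35, 9 of 70, 72 of 133 (days 161 to 294), 30 of 91, 30 of 91 and 122 of 183. With a baseline scan on day 1, PFS captures every such death before day 56, but misses deaths on 72/133 = 54% of the days between the day-161 and day-294 scans. The protocol accepts a baseline scan up to 21 days earlier. The first gap is then 56 + 21 = 77 days, of which 77 − 61 = 16 fall outside the window.

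**The case against.** Five points can be made for the SAP.

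- **The closing sentence suggests that deaths from progression are events.** This is a fair reading of intent for investigator TTP. But the sentence before it censors the same patients, and the central-read rule has no such sentence. It leaves a conflict to resolve.
- **Protocol 14.5.1 itself censors patients without progression at the last assessment.** True, but the event definition explicitly includes death from lymphoma and other deaths have their own rule. The general sentence does not override either.
- **The protocol defines no central-read TTP.** This stands. A radiology-only version is a legitimate choice if it is labelled and declared.
- **The SAP was written to Amendment 4, and the protocol supplied is Amendment 5.** The Amendment 4 wording cannot be checked. Against the supplied protocol the mismatch stands, and the SAP's internal ambiguity does not depend on the version.
- **The size rests on assumed shares.** This also stands. Few patients may be affected, because progression can be recorded at the end-of-study visit or at the scan planned about a month after early discontinuation. The model also omits other-cause deaths. Moving their censoring back to the last scan works, if anything, in the opposite direction, because it shrinks later risk sets.

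The consequence is limited: TTP is descriptive, ORR is unaffected, and PFS captures part of what TTP misses.

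**Conclusion.** The concern holds. Followed as written, the SAP does not estimate the protocol's TTP. It differs on the event and on the censoring date, and Section 12 declares neither.

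The direction is upward if any patient dies of lymphoma without documented progression; with none, the event counts agree. The true size is unknown. Over an assumed share of 0 to 30%, with an exponential TTP and a true median of 6 months, the median is overstated by 0 to 2.1 months and the 12-month proportion by 0 to 11.0 points. In the assumed 30-patient cohort with 0 to 4 such deaths, the 12-month overstatement is 0 to 13.3 points, depending on when they fall.

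This should be fixed, but no decision rule or primary conclusion depends on it.

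**What to change.** 1. In SAP 7.3.4.1, define the TTP event as the earlier of documented progression and death due to lymphoma, with the date of death as the event date. Censor only other-cause deaths, at the time of death. Delete the closing sentence or align it.
2. State how patients with no post-baseline assessment are handled.
3. Make clear that the cause-of-death query applies to every death. It now appears only under duration of response: "If the cause of death does not explicitly state whether death is related to progression of disease, a query will be raised".
4. For central-read TTP, either use the same rule, or label it progression-only, list it in Section 12 and report the protocol definition alongside.

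The cost is SAP wording, a Section 12 entry, a re-run of TTP and at most a few relatedness queries for non-responders; cause of death is already on the study completion page. TTP may come out slightly less favourable. Attributing a death to lymphoma is a judgement in an open-label study, so the deaths should be listed with their assigned cause.

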		-21 to -1	Day 1	Day 2	8 ± 1 day	15 ± 1 day	22 ± 1 day	1 ± 1 day	8 ± 1 day	15 ± 1 day	22 ± 1 day	28 ± 4 days	1 ± 1 day	8 ± 1 day	15 ± 1 day	22 ± 1 day	28 ± 4 days	1 st Follow-up + 4 weeks ± 2 days			Follow-up Visits 2 - 12 ¹
ADCC assessment	X																				
Tumor biopsy (cytogenetics) ³	X																				
Serum immunoglobulin levels		X ²				X ²				X ²					X ²		X	X		X	
Bone marrow aspiration & biopsy	X ⁹										X					X ¹⁰		X ^{10, 8}			
Body weight	X	X		X	X	X	X	X	X	X	X	X	X	X	X	X	X	X	X	X	X
Physical examination	X ¹¹	X ²				X					X ¹²					X ¹²	X ¹²	X ¹²	X	X	
Vital signs	X	X ¹³	X	X ¹³	X ¹³	X ¹³	X ¹³	X ¹³	X ¹³	X ¹³	X	X ¹³	X ¹³	X ¹³	X ¹³	X	X	X	X	X	
ECG	X	X ¹⁴						X ¹⁴	X ¹⁴	X ¹⁴					X ¹⁴					X	
AE assessment											-----continuous-----										
Baseline disease and response assessment (CT/PET) ¹⁵		X ^{2, 17}									X ¹⁷					X ¹⁷		X ^{8, 17}			
Additional Radiological evaluation ¹⁶		X ¹⁷									X ¹⁷					X ¹⁷		X ^{8, 17}			
Previous/Concomitant medication	X	X	X	X	X	X	X	X	X	X	X	X	X	X	X	X		X	X	X	

Abbreviations: ADCC = antibody-dependent cell-mediated cytotoxicity; AE = adverse event; β -HCG = beta-human chorionic gonadotropin; C2D22 = Cycle 2 Day 22; CT = computed tomography; ECG = electrocardiogram; ECOG = Eastern Cooperative Oncology Group; EOS = End of Study; FU= Follow-up; PET = positron emission tomography; SD = stable disease; WOCBP = woman of childbearing potential.

¹ The second and third FU Visit should be scheduled 6 weeks \pm 1 weeks following the previous visit, the fourth to sixth FU Visit should be scheduled 3 months \pm 2 weeks following the previous visit, further FU Visits should then be scheduled every 6 months.

² Before study drug administration.

³ Tumor biopsy/aspirates should be obtained if malignant lymph nodes are easily accessible.

⁴ Premedication for patients who do not experience infusion reactions during the first 3 infusions will be optional at the discretion of the investigator for subsequent infusions.

⁵ The PK sample will be taken before study drug administration; at the end of the infusion; and 1 hour, 4 hours, and 24 hours after end of first MOR00208 infusion. The sample taken on Day 2 (ie, 24 hours after end of first infusion) belongs formally to Day 1.

⁶ The PK sample will be taken before study drug administration and 1 hour after the end of MOR00208 infusion.

⁷ The PK sample will be taken at second and third follow-up visit only.

⁸ Not performed at third FU (no response assessment).

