9.2 Secondary Efficacy Analysis

All secondary efficacy analyses will be provided twice, based on the response assessment of the Investigator and based on the central review assessment.

The analysis of ORR as described in section 9.1 will be additionally be stratified by Fc γ RIIIa and Fc γ RIIa polymorphism.

Fc γ R subgroups will comprise the heterozygous population and each different homozygous population, as well as the combined heterozygous plus low affinity homozygous Fc γ R populations. Subgroups with fewer than five patients will not be analysed.

These stratifications will be done for the overall analysis population as well as by NHL subtype.

The overall stable disease rate will be analyzed analogously to the overall response rate as described in Sect. 9.1.

Time to progression and progression-free survival will be analyzed using Kaplan-Meier methods. Kaplan-Meier tables for progression-free survival and time to progression will contain number of patients, number of patients with an event (non-censored patients), percentage of patients with an event, median time [months], 25% and 75% quantile and 95%-

confidence intervals for median (Brookmeyer and Crowley, 1982).

Moreover, the percentage of patients having an event until 2, 4, 6, and 12 months together with the corresponding 95%-confidence intervals will be retrieved.

In the main analysis of PFS, only patients with radiologically confirmed progression or death within 2 months of the last radiological assessment will be counted as having had a PFS event. A sensitivity analysis will also be done in which patients who were withdrawn from the study because of disease progression will be included as having a PFS event, even in the absence of radiological confirmation of disease progression.

Duration of response and time to response (Investigator) and duration of best overall response and time to response (Central Read) will also be analyzed using Kaplan-Meier estimates for median, 25% and 75% quantile. The analysis of duration of response will be restricted to the subgroup of responders. Moreover, the percentage of patients having an event after 2, 4, 6, and 12 months together with the corresponding 95%-confidence intervals will be retrieved from the Kaplan Meier curve.

The analysis of duration of response and time to response will be presented for all responders overall.

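### The SAP's two-month limit censors deaths that the protocol counts as PFS events, even in patients scanned exactly on schedule

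*SAP*

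**What the plan says.** Protocol 10.6: "PFS is defined as the time from study entry (first dosing) until lymphoma progression or death as a result of any cause". Protocol 14.5.1 repeats this and limits censoring to those with neither event: "Patients not experiencing a progression or death will be censored at the last NHL assessment". Neither section sets a time limit on deaths.

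SAP 7.3.4.1 opens with the same any-cause definition and then narrows it. A death without documented progression counts if it falls within 2 months of the last tumor assessment. Otherwise ("If death occurs after 2 months after the last date with a tumor assessment") the patient is censored at that assessment. SAP 7.3.4.2 has the same rule for the central read. SAP 9.2 makes it the main analysis: "only patients with radiologically confirmed progression or death within 2 months of the last radiological assessment will be counted as having had a PFS event".

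The only PFS sensitivity analysis in SAP 9.2 adds a different group: "patients who were withdrawn from the study because of disease progression will be included as having a PFS event". SAP Section 12 lists three changes from the protocol: the PK population, central-read ORR ("The protocol did not specify ORR as a result of central read as an endpoint") and the dropped CD19 endpoint. The PFS rule is not among them.

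Protocol 10.3 sets the follow-up scans: "Response assessment should be repeated at 2nd, 4th, 5th and all subsequent follow-up visits and include" imaging. Footnote 1 of Protocol Table 2 sets the late spacing: "further FU Visits should then be scheduled every 6 months".

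**The concern.** A limit on late deaths is usually defended as a way to handle missed assessments: after a long unobserved stretch, the patient may have progressed unseen. That defence does not apply when the limit is shorter than the scheduled interval. Here a patient can attend every visit, die between two planned scans and still lose the event.

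The patient leaves the risk set because of the death, so the censoring is informative, and it favours longer PFS. It affects the investigator and central-read analyses, and the PFS subgroups and Cox hazard ratios in SAP 9.3. The reported PFS would not be the PFS that the protocol defines, no planned analysis would recover it, and the SAP section on changes would not tell the reader.

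**Working it through.** The documents state no PFS rate, event count or power, so there is no PFS figure to reproduce.

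**Limit.** SAP 7.1 converts months at 30.4375 days: L = 2 × 30.4375 = 60.9 days.

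**Scheduled scan times.** Days are counted from Cycle 1 Day 1. Cycle 2 Day 28 is day 55. Cycle 3 starts 2 weeks after Cycle 2 Day 22 (day 49 + 14 = 63), so Cycle 3 Day 28 is day 90. FU1 follows 4 weeks later, FU2 and FU3 at 6-week steps, FU4 to FU6 at 3-month steps, then every 6 months. FU1 and FU3 have no scan.

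| Gap | Days | Days beyond 60.9 | Share of gap |
|---|---|---|---|
| C1D1 to C2D28 | 55 | 0 | 0% |
| C2D28 to C3D28 | 35 | 0 | 0% |
| C3D28 to FU2 | 28 + 42 = 70 | 9.1 | 13% |
| FU2 to FU4 | 42 + 91.3 = 133.3 | 72.4 | 54% |
| FU4 to FU5 | 91.3 | 30.4 | 33% |
| FU5 to FU6 | 91.3 | 30.4 | 33% |
| FU6 to FU12 (6 gaps) | 182.6 each | 121.8 each | 67% |

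Only the C3D28 to FU2 gap can shrink below the limit: to 57 days, with every visit window at its extreme and the scan 4 days early. The first on-treatment gap could exceed the limit only if the baseline scan was more than about 6 days before Day 1 (60.9 − 55 = 5.9) and counts as a tumor assessment, which the SAP does not say.

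**Share of calendar time beyond the limit after C3D28** (shares of days, not of deaths):
- First 365 days: (9.1 + 72.4 + 30.4 + 9.5) / 365 = 33%
- First 730 days: 364.8 / 730 = 50%
- To FU12: 872.9 / 1,481.7 = 59%

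**Direction.** Suppose n patients are at risk at the last scan of a patient who later dies, k others have events before that death, and nobody else is censored. Just after the death, the Kaplan-Meier factor since that scan is (n − k − 1)/n under the protocol and (n − k − 1)/(n − 1) under the SAP. The SAP value is the larger.

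**Size, under assumed rates.** Let progression and death before documented progression be exponential, with progression dated at the next scheduled scan, all scans on time and no unscheduled scans. Write λ for the death rate. The protocol rule multiplies survival by exp(−λg) over a gap g. Under the SAP rule, patients who die late in the gap leave the risk set at its opening scan, so for g > L the factor becomes exp(−λg) / [1 − exp(−λL) + exp(−λg)].

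Middle case: progression median 9 months, death median 18 months.
- At 12 months the last scan is FU4 (day 293.3, 9.64 months). The progression factor is 2^(−9.64/9) = 0.476.
- Protocol: 2^(−12/18) = 0.630, so PFS = 0.476 × 0.630 = 30.0%.
- SAP: first 90 days 0.892, then gap factors 0.925, 0.919 and 0.923; product 0.701, so PFS = 0.476 × 0.701 = 33.4%.
- At 24 months the last scan is FU7 (21.64 months), with progression factor 0.189. Protocol: 0.189 × 0.397 = 7.5%. SAP: 0.189 × (0.701 × 0.923 × 0.915 × 0.915 = 0.541) = 10.2%.

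Simulation of 35 scenarios with 300,000 patients each crossed progression medians of 3 to 24 months with death rates of 0.5% to 5.8% per month:
- 12-month PFS rises by 0.2 to 6.2 points, and 24-month PFS by 0.0 to 7.8 points.
- The median is unchanged in 26 of 35.
- Of deaths without documented progression, 15% to 48% are censored, or 0.2 to 7.0 patients per 30.
- Low case (progression median 6 months, death 1% per month): a rise of 0.9 points at 12 months, from 0.9 patients per 30.

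**The case against.** The strongest objection is to the size. Nothing in the documents supports the assumed death rates. The middle case implies that 11.2 of 30 patients die without documented progression, and the most extreme implies 20.8 of 30. A shift of about 3 points is small beside the sampling error of one cohort: 1.96 × √(0.3 × 0.7 / 30) gives a half-width of about 16 points. Cohorts stopped after Stage 1 have only about 10 patients. The calculation also leaves out the analysis cutoff, other withdrawals, and deaths after withdrawal that may never be recorded. All of this stands as a caution on magnitude. None of it justifies the rule, and a bias does not shrink because the standard error is large.

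Second, SAP 7.3.4.1 says tumor assessment, not scan, and Protocol 10.3 has palpable tumor assessment at every follow-up visit. If FU1 and FU3 counted, the first-year share would fall from 33% to 19%, and the middle-case shift at 12 months from about 3.3 to about 1.4 points. The reading is weak: SAP 9.2 refers to radiological assessment for the main analysis, and both Table 2 footnote 8 and Protocol 10.3 exclude a response assessment at FU3. Footnote 16 read alone would suggest an FU3 scan and should be reconciled. On either reading the gaps from FU3 onward still exceed the limit.

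Third, the rule is stated openly in the SAP, and Protocol 14.13 requires deviations to be explained in the study report. That is true, but Section 12 is where the SAP lists its changes. The SAP cites protocol Amendment 4 while the protocol supplied is Amendment 5, so the PFS wording current when the SAP was written cannot be checked. The SAP's own any-cause opening still conflicts with its limit.

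**Conclusion.** The concern holds. The SAP departs from the protocol's PFS definition without listing the change, and its limit is shorter than every scheduled scan interval after Cycle 3. The mismatch, the gaps and the upward direction follow from the documents. The amount does not: it depends on how many patients die without documented progression, and ranges from negligible to about 6 points at 12 months under the assumptions shown. Unscheduled scans would reduce it. Deaths after documented progression are not affected, nor are on-treatment deaths when the baseline scan is on Day 1.

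This should be fixed, but it does not threaten the trial's main conclusion. PFS is secondary and no inference testing is planned; ORR, the futility rule and entry to Stage 2 do not depend on it.

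**What to change.** In SAP 7.3.4.1 and 7.3.4.2, replace the two-month rule with: 'A patient who dies without documented progression has a PFS event on the date of death. A patient with neither progression nor death is censored at the last tumor assessment, or at Cycle 1 Day 1 if there is no post-baseline assessment.' The Day 1 clause is a conventional default that neither document now contains. Change the main-analysis sentence in SAP 9.2 to match, and state whether a death after the start of other anti-tumor treatment counts.

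If censoring for missed assessments is still wanted, keep it as a sensitivity analysis, tie it to missed scheduled scans rather than a fixed two months, and list it in Section 12.

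The cost is wording in three places and a re-run of PFS and its subgroups. No new data are needed. PFS estimates will be slightly less favourable. SAP 4.1 already allows later analyses and an addendum to the study report, where the correction can be made.
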